3.1.1. Data Monitoring Committee

An independent DMC will review the available data on an ongoing basis throughout the study and before initiating a new cohort. The DMC will be composed of independent reviewers who are not involved in the conduct of the study. The DMC will advise the Sponsor of any trends or safety issues that may impact the study or study participants. In particular, the occurrence of any clinically significant AE (including but not limited to SAEs, AEs leading to study drug discontinuation/study withdrawal, dose-limiting toxicities [DLTs], and adverse events of special interest [AESIs], all considered at least possibly related to study drug) will receive special consideration (see [Section 7.2.5](#)). The Sponsor will make final decisions concerning the continuation, modification, or termination of the trial. The DMC's scope of responsibility, membership, confidentiality, and procedures will be established in a separate DMC charter. Three DMC reviews are planned during and upon completion of Cohorts 1-3. Three additional DMC reviews are planned during Cohorts 4-9. Ad hoc DMC meetings may be called by the Sponsor or the DMC Chair ([Figure 2](#)).

For Cohorts 1-3, the DMC will review safety data from a minimum of 2 sentinel participants for 2 weeks at each meeting. For Cohorts 4-9, the DMC will review safety data from a minimum of 4 sentinel participants at each meeting, but it is not required that 2 come from each cohort. However, to initiate a

new dosing regimen in a pediatric cohort, data from at least 2 pediatric sentinels must be included in the review.

3.1.2. Study Visits

Each participant will undergo a Screening Period of up to approximately 14 days, a 12-week (Cohorts 1 to 3) or 4-week Treatment Period (Cohorts 4 to 9), and a 30-day Safety Follow-up Period. The Screening Period may be extended as approved by the Sponsor and/or contract research organization (CRO) designee. The Schedule of Activities for the study is provided in [Appendix 1](#) and [Appendix 3](#) for Cohorts 1 to 3 and Cohorts 4 to 9, respectively. The Schedule of Activities for the extension is in [Appendix 2](#) and [Appendix 4](#), respectively.

3.1.2.1. Visit 1 (Screening)

Initial Screening will be conducted as an outpatient visit at approximately Day -14; the screening window may be extended with Sponsor/Medical Monitor (MM) approval. The following activities will be performed:

- Informed consent/assent and/or parent/legal guardian permission, as applicable (prior to undergoing any study procedures)
- Assessment of participant eligibility (Inclusion/Exclusion Criteria)
- Review of demographics, medical history, and medications (both current and from the past year)
- Hepatitis B, C, and human immunodeficiency virus (HIV) screening
- Pregnancy test for females of childbearing potential (FOCP) (serum)
- Screening/safety labs (see [Appendix 1](#) and [Appendix 3](#))
- Urinalysis
- Vital signs: blood pressure, pulse rate, body temperature, respiration rate, weight, and height (height is only measured during the Screening Visit).
- Physical exam (abbreviated/directed)
- 12-lead ECG
- Baseline Suicidality Questionnaire- Columbia–Suicide Severity Rating Scale (C-SSRS) (for participants aged ≥ 6 years only)
- Baseline Depression and Anxiety Questionnaires (Patient Reported Outcomes Measurement Information System [PROMIS] (for participants aged ≥ 5 years only) or Survey of Well-being of Young Children [SWYC] depending on age of participant)
- Bone age and predicted adult height calculated from x-ray image of left hand and wrist (if deemed appropriate by the principal investigator). Alternatively, a calculation using historical data is acceptable if image is within 6 months prior to screening. An x-ray may be repeated at the discretion of the Investigator. This will not be performed in adults (Cohorts 4 & 5).

3.1.2.2. Visit 2 (Day 1)

Visit 2 will be conducted as an outpatient visit during which a supervised first dose of tildacerfont will be administered after completion of a morning meal. The following activities will also be performed during the visit:

- Re-confirm participant meets inclusion/exclusion criteria
- Review concomitant medications for any changes
- Pregnancy test for FOCP (urine)
- For Cohorts 1, 2, 4, 5, 6, 7, 8, and 9 (and 1a if indicated), serial blood samples will be collected at 3 timepoints: pre-dose (prior to GC dosing and tildacerfont dosing), 0.5 to 1.5 hours post-GC and tildacerfont dose, and 3 to 5 hours post-GC and tildacerfont dose. After the pre-dose sample, participants will receive a meal and take their morning GC dose and study drug. Fasting is not required. Blood samples will be used to assess tildacerfont concentrations and to compare to the PBPK model, as well as PD markers including ACTH, 17-OHP, A4, testosterone, and 11KT.
 - Note: Cohorts 1 and 2 (and 1a if indicated) will receive study drug in the mornings for the first 14 days, so they will continue to take study drug at home with a morning meal until Day 14/Visit 3.
- For Cohorts 3 only one pre-dose sample will be drawn, after which participants will receive a meal and their morning GC dose and study drug. They should be observed for approximately 1 hour after receiving study drug.
 - Note: Cohort 3 will only receive the first dose of study drug in the morning to allow clinical observation. They will switch to home dosing with an evening meal on Day 2.
- Vital signs: blood pressure, pulse rate, body temperature, respiration rate, and weight (pre-dose)
- Physical exam (full)
- Safety labs (pre-dose, see [Appendix 1](#) and [Appendix 3](#))
- Dispense study drug (12-week or 4-week supply, depending on cohort)
- Assess for AEs

3.1.2.3. Visit 3 (Week 2; Day 14 ±3 days)

Visit 3 will be conducted as an outpatient visit. Cohorts 1, 2, 4, 5, 6, 7, 8, and 9 (and 1a if indicated) will receive study drug and morning GC dose after completion of a morning meal. Cohort 3 will have received study drug the evening prior and will not require supervised dosing or a meal. Note: Cohort 1, 2, 4, 5, 6, 7, 8 and 9 (and 1a, if indicated) participants will need to bring study drug to the visit for in-clinic dosing to collect tildacerfont concentrations. The following activities will also be performed during the visit:

- Review concomitant medications for any changes
- Pregnancy test for FOCP (urine)
- Safety labs (predose; see [Appendix 1](#) and [Appendix 3](#))
- For Cohorts 1, 2, 4, 5, 6, 7, 8, and 9 (and 1a, if indicated), serial blood samples will be collected at 3 timepoints: pre-dose (prior to GC dosing and tildacerfont dosing), 0.5 to 1.5 hours post-GC and tildacerfont dose, and 3 to 5 hours post-GC and tildacerfont dose. After the pre-dose sample, participants will receive a meal and take their morning GC dose and study drug. Fasting is not required. Blood samples will be used to assess tildacerfont concentrations and to compare to the PBPK model, as well as PD markers, including ACTH, 17-OHP, A4, testosterone, and 11KT.

- Note: Cohorts 1 and 2 (and 1a if indicated) will switch to evening dosing with a meal at home on Day 15.
- For Cohorts 3, only one pre-dose sample will be drawn, after which participants will receive their morning GC dose and tildacerfont dose. Fasting is not required. Blood samples will be used to assess tildacerfont concentrations as well as PD markers including ACTH, 17-OHP, A4, testosterone, and 11KT.
- Cortisol
- Urinalysis (pre-dose)
- Vital signs: blood pressure, pulse rate, body temperature, respiration rate, and weight (pre-dose)
- Physical exam (abbreviated/directed)
- 12-lead ECG (pre-dose)
- Suicidality Questionnaire- C-SSRS since last visit (participants aged ≥ 6 years only)
- Depression and Anxiety Questionnaires (PROMIS or SWYC depending on age of participant)
- Study drug accountability
- Assess for AEs

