5.2.4. Preparation and Administration

Participants will be taking between 1 and 6 tablets daily, depending on the dose and Cohort assignment. Participants can either swallow the tablet[s] whole or crush the tablet[s] and sprinkle on soft foods.

Cohorts 1 to 3 will receive doses QD. The dose will be taken with the evening meal. The first 2 weeks in Cohorts 1, 1a, and 2 will require dosing with a morning meal.

Cohorts 4-9 will receive BID dosing. Each dose should be taken with the morning and evening meal.

If necessary, the study drug may be taken up to 30 minutes after completing the meal(s) at home. If a participant has not consumed study drug within 30 minutes following the meal(s), the participant should consume study drug with a snack. Study drug will be dispensed at Day 1 for the duration of the study.

The Day 1 and Day 14 morning doses of tildacerfont will be administered in the clinic for Cohorts 1, 2, 4, 5, 6, 7, 8, and 9 (and 1a, if indicated) and Day 1 only for Cohort 3. Any remaining study drug will be returned for accountability at Visit 6 (Week 12) for Cohorts 1 to 3 and Visit 4 (Week 4) for Cohorts 4 to 9, any early termination (ET) Visits, and during extension visits. The Investigator is responsible for ensuring that dosing is administered in compliance with the protocol.

Preparation and administration instructions are included in the Pharmacy Manual.

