¹⁰ In all cohorts, GC dose (frequency or total daily dose) may be adjusted based on A4 levels collected at Weeks 4 and 8 (all participants) and Week 12 (for those participants continuing in the optional EP). If a change in GC is warranted by the A4 algorithm, sites will contact participants by telephone after receipt of results (within approximately 2 weeks) after each applicable study visit.

¹¹ Urinalysis should include the following: specific gravity, pH, glucose, protein, blood, ketones, bilirubin, urobilinogen, nitrite, by dipstick. Microscopic examination should be obtained if blood or protein is abnormal. For visits in which tildacerfont is administered, urinalysis should be performed pre-dose.

¹² Systolic and diastolic blood pressure, pulse rate, body temperature, and respiration rate. Height will only be collected at Screening.

¹³ Full physical exam is performed at Visit 2, Visit 6, and ET Visit; an abbreviated/directed physical exam is performed at all other visits.

¹⁴ Day 1 ECGs are conducted pre-dose. Day 14 ECG is dose independent, as participants should be at steady state.

¹⁵ Historical bone age and predicted adult height calculation may be used if performed \leq 6 months prior to Screening. If no appropriate image is available, x-ray of left hand and wrist will be performed to assess bone age and calculate predicted adult height.

¹⁶ The C-SSRS, to assess suicidality, is only conducted for participants aged 6 to 17 years.

¹⁷ PROMIS, to assess anxiety and depression, is conducted for participants aged 5 to 17 years.

¹⁸ The SWYC to assess anxiety and depression is only conducted in Cohort 3 participants \leq 5 years of age.

¹⁹ A 12-week supply of study drug will be dispensed at Visit 2 (Day 1). Participants should bring study drug to all visits for accountability. Upon receipt of study drug, the pharmacy will hold/store two doses to ensure that in-clinic dosing can occur at Visit 3 (Week 2) in the event a participant does not bring study drug to the visit.

²⁰ Cohorts 1 and 2 dosing:

Cohorts 1 and 2 (and 1a if indicated) will dose with a morning meal for the first 14 days of the study. Cohorts 1 and 2 (and 1a if indicated) will take the study drug at the clinic on Day 1 (Visit 2) (to allow for a 1-hour safety observational period and serial tildacerfont concentrations), and on Day 14 (to allow for serial tildacerfont concentrations).

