Starting on Day 15, Cohorts 1 and 2 will switch to taking the study drug with their evening meal for the duration of the study.

Cohort 3 dosing:

Cohort 3 will dose with a morning meal at the study clinic on Day 1 (Visit 2) to allow for a 1-hour observational period. All subsequent doses for Cohort 3 will occur with evening meals.

APPENDIX 2. SCHEDULE OF ACTIVITIES FOR OPEN-LABEL EXTENSION FOR COHORTS 1, 1A, 2, AND 3

	Week 12	Week 24	Week 36	Week 48	Week 60	Week 72	Week 84	Week 96 (EOT)	Early Termination	Safety Follow-up (Phone call)
VISIT NUMBER	6	7	8	9	10	11	12	13		
Visit windows	±2 weeks		Last dose +30 days							
Informed consent/assent	X									
Concomitant medications	X	X	X	X	X	X	X	X	X	X
Pregnancy test for FOCP ¹	X	X	X	X	X	X	X	X	X	
Laboratory assessments ^{2,3}	X	X	X	X	X	X	X	X	X	X ⁴
PD and tildacerfont samples ⁵	X	X	X	X	X	X	X	X	X	X ⁴
A4-based GC dose adjustment ⁶	X	X	X	X	X	X	X	X		
Weight-based tildacerfont dose adjustment	X	X	X	X	X	X	X	X		
Urinalysis ⁷				X		X		X	X	X ⁴
Vital signs ⁸ , body weight	X	X	X	X	X	X	X	X	X	X ⁴
Abbreviated/directed physical exam	X	X	X	X	X	X	X	X	X	X ⁴
C-SSRS ⁹	X	X	X	X	X	X	X	X	X	X ⁴
PROMIS ¹⁰	X	X	X	X	X	X	X	X	X	X ⁴
SWYC ¹¹	X	X	X	X	X	X	X	X	X	

SPR001-205

Spruce Biosciences, Inc.

CLINICAL STUDY PROTOCOL

Version 5.0

	Week 12	Week 24	Week 36	Week 48	Week 60	Week 72	Week 84	Week 96 (EOT)	Early Termination	Safety Follow- up (Phone call)
VISIT NUMBER	6	7	8	9	10	11	12	13		
Visit windows	±2 weeks		Last dose +30 days							
Bone age and predicted adult height ¹²		X		X		X		X		
Dispense study drug	X	X	X	X	X	X	X	X		
Review any AEs	X	X	X	X	X	X	X	X	X	X
Study drug accountability	X	X	X	X	X	X	X	X	X	

Abbreviations: 11KT=11-ketotestosterone; A4=androstenedione; ACTH=adrenocorticotropin hormone; AEs=adverse events; ALT=alanine aminotransferase; ALP=alkaline phosphatase; AST=aspartate aminotransferase; C-SSRS=Columbia–Suicide Severity Rating Scale; ECG=electrocardiogram; EOT= end of treatment; ET=early termination; FOCP=female of childbearing potential; GC=glucocorticoid; GGT=gamma-glutamyl transferase; PD=pharmacodynamics; PROMIS= Patient Reported Outcomes Measurement Information System; 17-OHP=17-hydroxyprogesterone; SWYC=Survey of Well-being of Young Children; T=testosterone.

¹ A serum pregnancy test will be performed at Screening for FOCP only. All subsequent tests will be urine pregnancy tests

² Labs will be drawn at 8 AM (±1 h) before any morning dose of GC medication.

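### For the once-daily Cohorts 1, 1a and 2, the Visit 3 window (Days 11-17) overruns the fixed Day 15 switch to evening dosing, and no text says which governs a late visit

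*Protocol*

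**What the plan says.** - **Frequency.** Protocol Section 5.2.4: "Cohorts 1 to 3 will receive doses QD".
- **Visit 3.** Section 3.1.2.3 and Appendix 1 set the visit at Day 14 with three days either side. Cohorts 1, 1a and 2 "will receive study drug and morning GC dose after completion of a morning meal", with a sample before the dose and two after it. The instruction is the same on every day of the window.
- **Switch as a fixed day.** Section 3.1.2.3: "Cohorts 1 and 2 (and 1a if indicated) will switch to evening dosing with a meal at home on Day 15". Appendix 1 footnote 20 says these cohorts "will dose with a morning meal for the first 14 days of the study", and then: "Starting on Day 15, Cohorts 1 and 2 will switch to taking the study drug with their evening meal". The SAP repeats this under Table 8.
- **Switch possibly tied to the visit.** Section 3.1.2.2, in a note on Cohorts 1, 1a and 2: "they will continue to take study drug at home with a morning meal until Day 14/Visit 3". Sections 5.2.4 and 5.3.1.1 also use Day 14 as the name of the second clinic dose.
- **Use of the samples.** The Week 2 concentrations feed the secondary comparison with the PBPK simulation. SAP Table 7 puts the Week 2 target at Study Day 15, with an analysis window of Days 9-22.

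**The concern.** A site that sees a participant on Day 15, 16 or 17 is within the visit window, but it holds two instructions that do not fit together. It must give a morning dose in clinic, while the calendar rule has already moved the participant to evenings. Two sites could each follow the protocol and dose differently.

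Two things are at stake. One is dose spacing in 11- to 17-year-olds on a once-daily regimen. The other is the meaning of the Week 2 pre-dose sample. Week 2 is the only serial multiple-dose sampling in these cohorts, and a trough taken half a day after a dose is not the trough of a 24-h regimen. SAP Table 7 would place such a sample in the same Week 2 bin as the others.

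**Working it through.** **Inputs from the documents.** Visit 3 on Days 11-17 (14 − 3 to 14 + 3, seven days); pre-dose sample at about 8 AM; once-daily dosing; morning doses through Day 14; evening doses from Day 15.

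**Assumptions.** The documents give no clock time for the evening meal, so I take 17:00-20:00. I take the sample at 08:00 and morning doses at 08:30.

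**Switch fixed at Day 15:**

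| Visit 3 on | Last dose before sample | Sample, hours after that dose | Gap, last dose to clinic dose | Gap, clinic dose to next dose |
|---|---|---|---|---|
| Days 11-13 | previous morning | 23.5 | 24 | 24 |
| Day 14 | Day 13 morning | 23.5 | 24 | 32.5-35.5 |
| Day 15 | Day 14 morning | 23.5 | 24 | 8.5-11.5 |
| Days 16, 17 | previous evening | 12-15 | 12.5-15.5 | 8.5-11.5 |

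- Sample on Days 16-17: 20:00 to 08:00 is 12 h; 17:00 to 08:00 is 15 h.
- Clinic dose on Days 16-17: 20:00 to 08:30 is 12.5 h; 17:00 to 08:30 is 15.5 h.
- Next evening dose: 08:30 to 17:00 is 8.5 h; 08:30 to 20:00 is 11.5 h.
- On Days 16-17 the two gaps add to 24 h (12.5 + 11.5, or 15.5 + 8.5), so the previous evening, clinic and same-evening doses fall within one 24-h span.

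Three of the seven permitted days (15, 16, 17) conflict with the fixed switch. Two of them (16, 17) change the pre-dose sample. On Day 15 all three samples are taken before the extra evening dose.

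**Switch on the day after Visit 3.** For every visit day from 11 to 17 the sample is 23.5 h after the last dose and there is one dose that day. The conflict disappears. For visits on Days 11-13, however, this reading moves the switch to Days 12-14, which does not match the 14 days of morning dosing in Appendix 1.

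**Size of the PK shift on Days 16-17.** The documents give no half-life h, so I show a range. I assume first-order decay, instantaneous absorption and equal doses. Let Δ be the hours from last dose to sample, and n the number of evening doses already taken (1 for Day 16, 2 for Day 17). The switch itself leaves a gap of 32.5-35.5 h, which lowers what earlier doses contribute. Relative to the 23.5-h trough on continued morning dosing:

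ratio = 1 + (2^((23.5 − Δ)/h) − 1) × (1 − 2^(−24n/h))

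| h (assumed) | Lowest: Day 16, Δ = 15 | Highest: Day 17, Δ = 12 |
|---|---|---|
| 12 h | 1 + 0.634 × 0.750 = 1.48 | 1 + 0.943 × 0.938 = 1.88 |
| 24 h | 1 + 0.278 × 0.500 = 1.14 | 1 + 0.394 × 0.750 = 1.30 |
| 40 h | 1 + 0.159 × 0.340 = 1.05 | 1 + 0.221 × 0.565 = 1.12 |

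The shift is upward in each case: large if the half-life is short, small if it is long.

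**The case against.** The strongest reply is that Day 14 is simply the protocol's name for Visit 3, and Day 15 means the day after it. Sections 3.1.2.2, 5.2.4 and 5.3.1.1 and footnote 20 all support that usage, and once-daily dosing argues against a two-dose day. This stands as a reasonable reading. It does not settle the matter, because the same footnote counts 14 days and no sentence covers a visit held after Day 14.

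A reader might infer that any visit on Days 15-17 spoils the pre-dose sample. The documents do not support that: on Day 15 the last dose is still the previous morning's. Nor do they support an unavoidable double dose, since that follows only from the literal reading.

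A reader might also infer that the PBPK comparison is biased. That is not shown. Protocol Section 8.3.5 defers that work to a pharmacometrics plan outside these documents, which may already use actual dose times. It must in any case handle varied times since dose, because the 8 AM samples at Weeks 4, 8 and 12 follow evening dosing by design. The documents also do not establish that dose times went unrecorded. Protocol Section 1.2.3 already reports that the model overestimates exposure in children; an upward shift in some samples would partly mask that finding, not create it.

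Finally, little may remain to change prospectively. Section 1.2.3 counts 30 children treated in Cohorts 1-3 by 1 November 2023, against a planned maximum of 25, and Section 1.2.1 treats the Cohort 2 dose as already studied. That limits the value of a new visit window, but not of a rule for data already collected.

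**Conclusion.** The concern holds as an unreconciled conflict between a visit window and a fixed switch day, confined to Cohorts 1, 1a and 2. Under the literal reading it affects dose spacing on three of the seven permitted visit days and the pre-dose sample on two. The intervals rest on an assumed evening meal at 17:00-20:00. The PK ratio of about 1.05 to 1.9 rests on assumed half-lives of 12-40 h and a simple decay model, and may be modest. Planned enrolment in these cohorts is up to 15 (5 + 5 + 5), but the number with a Visit 3 after Day 14 is unknown and could be nil. The definition of the primary endpoint is untouched. The matter deserves correction because a stated rule gives a wrong result inside its own window and the remedy is cheap; the documents do not show that harm or bias occurred.

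**What to change.** 1. **Reconcile the text.** The sponsor should bring Protocol Sections 3.1.2.2, 3.1.2.3, 5.2.4 and 5.3.1.1, Appendix 1 with footnote 20, and SAP Table 8 with its footnotes into agreement, so that the Visit 3 window and the switch day cannot conflict. Which dosing instruction governs is for the sponsor to decide.
2. **One route that sets no dosing rule.** For Cohorts 1, 1a and 2, limit the Visit 3 assessment window so that serial sampling precedes the switch, for example −3/+0 days (Days 11-14). The cost is a narrower window, four permitted days instead of seven. It does not cover visits held late out of window, and it does not replace step 1.
3. **Data already collected.** In the pharmacometric analysis, use the actual time of the previous dose, flag Visit 3 samples taken on Days 16-17, and do not compare any that followed an evening dose with the simulated 24-h once-daily profile. Report how many there were. The cost is one analysis rule, which the separate plan may already contain.

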5.3.1. Glucocorticoid Replacement Therapy

5.3.1.1. General Procedures for Glucocorticoids

Concomitant medications include GCs. Information to be collected at Screening about a participant's current and prior GC therapy for the past month include the type(s) of GC, the regimen(s), and any GC stress dosing during the past month.

To be eligible for this study, participants must be on a stable dose of GC replacement for ≥ 1 month before Screening without evidence of non-adherence (standard of care weight-based dose adjustments

and stress dosing are allowed). Participants with the salt-wasting form of CAH who take mineralocorticoids must also be on a stable dose of mineralocorticoid replacement for ≥ 1 month before Screening.

On the mornings of all study visits, including the Screening Visit, participants should delay taking any morning dose of GC medication. On Day 1 all participants will receive a supervised tildacortal dose in clinic and can take their morning GC dose at that time (after the pre-dose assessments). The same applies to Cohorts 1, 2, 4, 5, 6, 7, 8, and 9 (and 1a if indicated) for Day 14. On all other visits, participants can take their morning GC dose after completion of the 8 AM (± 1 hour) assessments (PK, PD, and safety). On all other non-clinic visit days during the study, participants should take their GC medication at the usual time(s). Mineralocorticoid may be taken at any time of day, but its timing relative to laboratory assessments should be consistent throughout the study.

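### Protocol 3.1.2.3 gives Cohort 3 (2 to 10 years, QD) two incompatible Week 2 dosing instructions; read literally, one adds a tildacerfont dose about 10 to 16 hours after the evening dose

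*Protocol*

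**What the plan says.** Both instructions are in Protocol 3.1.2.3 (Visit 3, Week 2) and concern the same cohort.

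- Opening paragraph: "Cohort 3 will have received study drug the evening prior and will not require supervised dosing or a meal".
- Cohort 3 bullet: after the single sample is drawn, "after which participants will receive their morning GC dose and tildacerfont dose".

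Other text on Cohort 3 dosing:

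- Protocol 3.1.2.2 (Day 1): "Cohort 3 will only receive the first dose of study drug in the morning to allow clinical observation", followed by "They will switch to home dosing with an evening meal on Day 2".
- Protocol 5.2.4, on in-clinic administration: Days 1 and 14 for the other cohorts, "and Day 1 only for Cohort 3".
- Protocol 5.3.1.1, after describing supervised dosing on Day 1: "The same applies to Cohorts 1, 2, 4, 5, 6, 7, 8, and 9 (and 1a if indicated) for Day 14". Cohort 3 is not in that list.
- Protocol Appendix 1, footnote 20: "All subsequent doses for Cohort 3 will occur with evening meals". SAP 5.2.1 and the matching footnote to SAP Table 8 say the same in substance.
- Protocol Synopsis, paragraph on PD and concentration sampling for Cohort 3: it covers every visit and says that morning GC and morning tildacerfont are both withheld until blood has been drawn. This presupposes a morning tildacerfont dose.
- Protocol Appendix 1, footnote 19: participants bring study drug to all visits, and the pharmacy keeps back two doses so that clinic dosing at Week 2 is possible. Cohort 3 is not excepted.

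**The concern.** The bullet is a step in a visit checklist, and a coordinator works from that list on the day. A site that follows it would dose a child aged 2 to 10 who is on a once-daily regimen and who, by the opening paragraph, was dosed the evening before. Footnote 19 means that drug would be on hand.

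The bullet also drops the meal. The Day 1 bullet for this cohort (3.1.2.2) gives a meal before the dose; the Week 2 bullet does not, and the opening paragraph says none is needed. Protocol 1.2.3 reports a food effect and says that development is conducted in the fed state.

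The PK stake is narrower. Comparison of plasma concentrations with the PBPK simulation is a secondary endpoint for Cohorts 1 to 3 (Protocol Section 2). For Cohort 3 it rests on single samples, and a single sample can be compared only if the time of the preceding dose is known. Two conflicting instructions leave that time uncertain.

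**Working it through.** The plan states no figure for the interval, so there is none to reproduce. The check sets the texts side by side and then works out the interval.

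**Side by side**

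| Text | What it implies for Cohort 3 at Week 2 |
|---|---|
| 3.1.2.3, opening paragraph | Dosed the evening before; supervised dosing not required |
| 3.1.2.3, Cohort 3 bullet | Tildacerfont given after the draw |
| 3.1.2.2; 5.2.4; 5.3.1.1; Appendix 1 footnote 20; SAP 5.2.1; SAP Table 8 footnote 20 | Fit the opening paragraph |
| Synopsis, Cohort 3 sampling paragraph | Leans towards the bullet |
| Appendix 1 footnote 19 | Makes drug available for clinic dosing, no exception for Cohort 3 |

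**Interval if the bullet is followed**

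Inputs:
- Morning draw: 8 AM ±1 hour, so 07:00 to 09:00 (Protocol 5.3.1.1).
- Evening meal: time not given; 17:00 to 21:00 is assumed.
- Regimen: QD with the evening meal (Protocol 5.2.4), so nominally 24 hours between doses.

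Formula: hours since the evening dose = (24 − evening time) + draw time, with the disputed dose taken at the time of the draw.

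| Evening dose | Draw 07:00 | Draw 08:00 | Draw 09:00 |
|---|---|---|---|
| 17:00 | 14 | 15 | 16 |
| 18:00 | 13 | 14 | 15 |
| 19:00 | 12 | 13 | 14 |
| 20:00 | 11 | 12 | 13 |
| 21:00 | 10 | 11 | 12 |

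The range is 10 to 16 hours. As a cross-check, exclusion criterion 10d (Protocol 4.1.2) allows certain morning medicines if they are about 10 hours from the evening study dose. That implies 24 − 10 = about 14 hours from evening to the next morning.

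If the usual evening dose on the visit day is also taken, the next gap is evening time − draw time: from 17 − 9 = 8 hours to 21 − 7 = 14 hours. There would then be three doses between one evening and the next, inclusive, where the regimen has two.

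**Effect on the Week 2 sample**

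The bullet fixes the order: "only one pre-dose sample will be drawn, after which participants will receive their morning GC dose and tildacerfont dose". Protocol Table 8 likewise lists a single Week 2 sample for Cohort 3. The disputed dose comes after the draw, so it cannot change that concentration.

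What can vary is the time since the previous dose. If the evening dose was taken, the sample is 10 to 16 hours after it. If a family expecting a morning dose skipped that evening, the last dose was one day earlier: 24 + 10 = 34 to 24 + 16 = 40 hours before the sample. The two cases are not comparable with the same simulated time point.

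**The case against.** The strongest reply is that the rest of the protocol mostly points one way. Six places fit the opening paragraph. Within 3.1.2.3 itself, the reminder to bring drug for clinic dosing leaves out Cohort 3. The bullet resembles its Day 1 counterpart without the meal, so it may be a carry-over. All of this is fair, but it does not remove the conflict: the bullet is operative, the Synopsis leans towards it, and footnote 19 makes it practicable. Counting passages does not tell a site what to do.

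The reply is right to limit the consequences. A reader might infer any of the following, and the documents do not support them:

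- *That the Week 2 concentration is distorted.* The sample precedes the disputed dose. The next scheduled sample is at Week 4, nominally 14 days later. No half-life is given, and exclusion criterion 9 accepts at least 2 weeks off tildacerfont as washout, so there is no stated basis for expecting one extra dose to carry through.
- *That the dosing rhythm changes from then on.* The bullet concerns one visit; other sections place later doses in the evening.
- *That the gap is about 12 hours.* No such figure appears. It is one value within a range that depends on an unstated meal time.
- *That the child receives twice the daily amount on the visit day.* The previous evening's dose belongs to the day before. Two doses fall on the visit day only if that evening's dose is also taken.
- *That 3.1.2.3 itself forbids clinic dosing.* Its opening paragraph says supervised dosing is not required. The firmer Day 1 limit is in 5.2.4.
- *That children were dosed twice.* No document shows it.

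It can also be said that clarification comes late. Protocol 1.2.3 reports 30 pediatric participants in Cohorts 1 to 3 by 1 November 2023, against 20 to 25 planned, so few Cohort 3 Week 2 visits may remain. That shifts weight to checking records; it does not make the check unnecessary.

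**Conclusion.** The contradiction is real and should be resolved. It is an internal inconsistency in a dosing instruction for children aged 2 to 10, and the bullet and the opening paragraph cannot both be carried out. Followed literally, the bullet puts a further dose 10 to 16 hours after the evening dose, or about 14 by the protocol's own spacing, where the regimen implies about 24, and with no meal provided. The range rests on the assumed 17:00 to 21:00 evening meal; every value in it is well short of 24 hours.

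For PK, the concern is limited to uncertainty about the actual time of the last dose before the Week 2 sample. Exposure is limited to Cohort 3, planned at about 10 participants; that is a cohort size, not a count of affected children.

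The planned outputs may not settle what happened. SAP Section 15 says that limitations in exposure and accountability data rule out exposure summaries, and SAP 12.1 describes listings of tablet counts and doses, with no mention of dose times.

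**What to change.** 1. Reconcile the opening paragraph and the Cohort 3 bullet of Protocol 3.1.2.3 with each other and with the Synopsis sampling paragraph, 3.1.2.2, 5.2.4, 5.3.1.1 and Appendix 1 footnotes 19 and 20. Carry the result into SAP 5.2.1 and the SAP Table 8 footnotes. Which instruction stands is for the sponsor to decide; this review takes no position.
2. Check source dosing records of completed Cohort 3 Week 2 visits for extra or mistimed doses, including a skipped dose the evening before. Use actual dose times in the PBPK comparison, and record any extra dose in the individual exposure listings (SAP 12.1).

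The cost is a short text clarification, handled under Protocol 9.10, and a record check for a cohort planned at about 10 participants. No endpoint, analysis set or sample size changes.
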